3.3 Data Source/Data Collection Process

The study timelines are presented in the picture below:

Figure 3.3-1: Study Timelines

[figure not shown]

Table 3.3-1: Study Registers

Register	Register Holder	Information obtained
National Prescription Register	Kela – The Social Insurance Institution of Finland	Drug purchases (ATC codes)
National Reimbursement Register	Kela	Reimbursement decisions 207 for chronic arrhythmias (for population characterization)
Finnish Care Register, HILMO	National Institute for Health and Welfare	Diagnoses (ICD10 codes) and date of diagnosis
National Causes of Death Register	Statistics Finland	Time of death and causes of death (ICD-10 codes)
Laboratory databases	HUSLAB + other hospital laboratories	INR measurements and other relevant laboratory values
Finnish Cancer Registry	National Institute for Health and Welfare	Cancer diagnosis (ICD-O-3 codes) and date of diagnosis
Population Register	Population Register Center	Places of domicile 12 months prior to and on index dates.
Social HILMO	National Institute for Health and Welfare	Information (dates) about institutionalization (other than hospitalization)

- Data will be requested from the registry holders ([Table 3.3-1](#)) based on the study protocol.
- Data permits will be requested from each registry holder based on the study protocol and ethical approval.
- Approval of Ethical Review Board of Hospital District of Helsinki and Uusimaa (HUS) will be requested to cover the nationwide study.
- This is a fully register-based study and patients will not be contacted in any phase of the study.
- Warfarin exposure will be defined by Kela, who then will convert the patient IDs to study IDs (SIDs). Kela will then send the IDs and the SIDs to other register holders: Statistics Finland, National Institute for Health and Welfare, Statistics Finland, Population Register Center, and central hospital laboratories included in the study.
- EPID Research will receive unidentifiable data including SIDs only. All patient data handled by the researchers are then anonymous which ensures full data protection of the patients.

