3.4.2 Exposure/Independent Variables of Interest

- Performance of warfarin therapy
 - INR values under 2.0, 2.0-3.0, and over 3.0
 - time to reach the target INR 2.0–3.0
 - TTR, percentage of time during which the interpolated INR values lie between 2.0 and 3.0¹³
- Exposure to warfarin (ATC B01AA03)
 - new vs. prevalent users (< vs. > 90 days)
 - time since discontinuation
- I48 diagnosis
 - yes/no
 - time from the diagnosis
- Place of domicile 12 months prior to and on the index date
 - if not in Finland, excluded
- Use of antiarrhythmic drugs:
 - yes/no
 - ◆ Group C01B: antiarrhythmic drugs, classes I and III (see [Appendix 3, Table 1](#) for details)
 - ◆ Group C07: beta blockers / class II antiarrhythmics (see [Appendix 3, Table 2](#) for details)
 - ◆ C08DB01: diltiazem (class IV antiarrhythmic)
 - ◆ C08DA01: verapamil (class IV antiarrhythmic)
- Use of other anticoagulant or reimbursed antithrombotic therapy:
 - heparins (B01AB01, B01AB51), clopidogrel (B01AC04), dipyridamole (B01AC07), ticlopidine (B01AC05), prasugrel (B01AC22)

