4.1.2 Secondary Objectives

Objective 1: Stratified incidence rates with 95% CIs will be estimated for stroke, systemic thromboembolic events, myocardial infarction, and bleeding events within the strata of the exposure variables (INR levels and TTR categories) and other covariates during the first 90 days after initiation of warfarin treatment.

The crude and adjusted hazard ratio (HR) estimates with 95% CIs and P-values will be estimated separately within the INR levels and TTR categories using the conventional Cox's proportional hazards model adjusting for other covariates, including history of AF prior the index date. For INR the category 2.0–3.0 will be used as the reference category. Similarly for TTR the category $\geq 60\%$ of time will be used as the reference category.

Objective 2: Stratified incidence rates with 95% CIs will be estimated for stroke, systemic thromboembolic events, myocardial infarction, and bleeding events within the strata of the exposure variables (INR levels and TTR categories), and time from AF diagnosis to time of initiation of warfarin treatment (categories: under 6 months, 6-12 months, over 12 months). For INR the category 2.0–3.0 will be used as the reference category. Similarly for TTR the category $\geq 60\%$ of time will be used as the reference category.

Also, time from AF diagnosis to time of initiation of warfarin treatment will be added as an additional covariate to the Cox's proportional hazards model.

Objective 3: Stratified incidence rates with 95% CIs will be estimated for stroke, systemic thromboembolic events, myocardial infarction, and bleeding events within the strata of other covariates for warfarin patients after stopping warfarin treatment. Warfarin treatment is considered ended if there is more than 2 months gap since last warfarin exposure and INR measurement. Sensitivity analysis with 1 and 3 months gaps will be performed to study the robustness of the definition.

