4.1.3 Exploratory Objectives

Objective 1: Stratified incidence rates with 95% CIs will be estimated for anemia as endpoint within the strata of the exposure variables (INR levels and TTR categories) and other covariates.

The crude and adjusted hazard ratio (HR) estimates with 95% CIs and P-values will be estimated separately within the INR levels and TTR categories using the conventional Cox's proportional hazards model adjusting for other covariates. For INR the category 2.0–3.0 will be used as the reference category. Similarly for TTR the category $\geq 60\%$ of time will be used as the reference category.

Objective 2: Discontinuity period of warfarin treatment due to a surgical operation or intervention is identified as starting two weeks before and ending two weeks after such procedure.

Stratified incidence rates with 95% CIs will be estimated for stroke, systemic thromboembolic events, myocardial infarction, and bleeding events in the strata of other covariates within periods of warfarin discontinuity. Also, an indicator variable of the discontinuity period will be added to the Cox's proportional hazards model.

Sensitivity analysis will be done to study the robustness of the discontinuity period definition.

Objective 3: The distribution of days taken to achieve INR target in the new warfarin user population will be provided. Stable INR-target is considered achieved after 3 consecutive INR measurements are within the target 2.0-3.0.

Objective 4: For the new warfarin user population the distribution of TTR at 1, 6, and 12 months after start of warfarin treatment stratified by other covariates. For the prevalent warfarin user population the distribution of TTR at the end of 2010 and 2011 stratified by other covariates.

Objective 5: Warfarin users will be tabulated by use of antiarrhythmic medication (yes/no) at start of follow-up and during follow-up. During follow-up users will also be stratified by the INR and the TTR levels.

Objective 6: Warfarin users will be tabulated by use of interaction medication (yes/no) at start of follow-up and during follow-up. During follow-up users will also be stratified by the INR and the TTR levels.

Objective 7: Warfarin users will be tabulated by comorbidities.

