5 STUDY LIMITATIONS/STRENGTHS

Finland has a well-developed population register system with tens of years of longitudinal follow-up data. The persons are identified in the registers with a unique personal identification number enabling linkage between different registers. These data has not been collected for study purposes, which may affect the quality of the data. However, these registers have been considered reliable for scientific research purposes.

Only those citizens that have been living in Finland for 12 months prior to index date will be included in the study.

No exact prescribed dosing information is available. Dosing is assumed based on the information of purchases and package sizes with defined daily doses (DDDs).

Coverage of the Prescription Register containing reimbursement information of all permanent residents of Finland is about 97%. Missing data includes relatively inexpensive packages which are not reimbursed. Fully reliable information on eg, acetylsalicylic acid use is then not available.

Medications used during hospitalizations are not available. However, based on the hospital care register the hospitalization periods can be taken into account to define gaps in the drug treatment periods.

No nationwide database about laboratory measurements is available. The laboratory data is then collected from separate local central laboratories. All laboratory values for particular patients may then not be available. Also changes in places of domicile may affect the follow-up of the patients. On the other hand, previous published surveys on the subject have not included INR follow-up to this extend.

To avoid selection bias, the cohort time (years 2007 to 2009) was chosen to avoid complication of patients switching from warfarin to newer anticoagulant medications eg, dabigatran.

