APPENDIX 3 ATCS INCLUDED IN THE STUDY

Possible changes in the ATC code during the study period are taken into account by Kela – The Social Insurance Institution of Finland.

B01AA03: warfarin

Antiarrhythmics:

Group C01B: antiarrhythmics, classes I and III (listed in detail in Table 1)

Group C07: beta blockers / class II antiarrhythmics (listed detail in [Table 2](#))

C08DB01: diltiazem (class IV antiarrhythmic)

C08DA01: verapamil (class IV antiarrhythmic)

C01EB10: adenosine (other type antiarrhythmic)

Table 1: C01B ANTIARRHYTHMICS, CLASS I AND III

C01BA Antiarrhythmics, class Ia	
C01BA01	quinidine
C01BA02	procainamide
C01BA03	disopyramide
C01BA04	sparteine
C01BA05	ajmaline
C01BA08	prajmaline
C01BA12	lorajmine
C01BA51	quinidine, combinations excl. psycholeptics
C01BA71	quinidine, combinations with psycholeptics
C01BB Antiarrhythmics, class Ib	
C01BB01	lidocaine
C01BB02	mexiletine
C01BB03	tocainide
C01BB04	aprindine
C01BC Antiarrhythmics, class Ic	
C01BC03	propafenone
C01BC04	flecainide
C01BC07	lorcainide
C01BC08	encainide
C01BD Antiarrhythmics, class III	
C01BD01	amiodarone
C01BD02	bretylum tosilate
C01BD03	bunaftine
C01BD04	dofetilide
C01BD05	ibutilide
C01BD06	tedisamil
C01BD07	dronedarone
C01BG Other antiarrhythmics, class I and III	
C01BG01	moracizine
C01BG07	cibenzoline
C01BG11	vernakalant

Table 2: C07A BETA BLOCKING AGENTS

C07AA Beta blocking agents, non-selective	
C07AA01	alprenolol
C07AA02	oxprenolol
C07AA03	pindolol
C07AA05	propranolol
C07AA06	timolol
C07AA07	sotalol
C07AA12	nadolol
C07AA14	mepindolol
C07AA15	carteolol
C07AA16	tertatolol
C07AA17	bopindolol
C07AA19	bupranolol
C07AA23	penbutolol
C07AA27	cloranolol
C07AA57	sotalol, combinations
C07AB Beta blocking agents, selective	
C07AB01	practolol
C07AB02	metoprolol
C07AB03	atenolol
C07AB04	acebutolol
C07AB05	betaxolol
C07AB06	bevantolol
C07AB07	bisoprolol
C07AB08	celiprolol
C07AB09	esmolol
C07AB10	epanolol
C07AB11	s-atenolol
C07AB12	nebivolol
C07AB13	talinolol
C07AB52	metoprolol, combinations
C07AB57	bisoprolol, combinations
C07AG Alpha and beta blocking agents	
C07AG01	labetalol
C07AG02	carvedilol
C07B BETA BLOCKING AGENTS AND THIAZIDES	
C07BA Beta blocking agents, non-selective, and thiazides	
C07BA02	oxprenolol and thiazides
C07BA05	propranolol and thiazides
C07BA06	timolol and thiazides
C07BA07	sotalol and thiazides
C07BA12	nadolol and thiazides
C07BA68	metipranolol and thiazides, combinations
C07BB Beta blocking agents, selective, and thiazides	
C07BB02	metoprolol and thiazides

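### The heparins variable in section 3.4.2 lists one substance and its combinations, so outpatient purchases of other heparins, including low-molecular-weight heparins, would be coded as no heparin

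*Protocol*

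**What the plan says.** Among the exposure variables of interest, Protocol section 3.4.2 has one headed "Use of other anticoagulant or reimbursed antithrombotic therapy". Its content is a single list: "heparins (B01AB01, B01AB51), clopidogrel (B01AC04), dipyridamole (B01AC07), ticlopidine (B01AC05), prasugrel (B01AC22".

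The same section can write a whole class when it means one, for example "Group C07: beta blockers / class II antiarrhythmics", with the members set out in Appendix 3.

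The only source of drug exposure in Table 3.3-1 is the National Prescription Register, which supplies "Drug purchases (ATC codes"). Section 5 adds: "Medications used during hospitalizations are not available". Section 3.3 says that data are requested from the register holders, and permits sought, on the basis of the protocol.

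Three planned analyses cover periods when warfarin is being started, stopped or interrupted:
- Secondary objective 1 (section 4.1.2) estimates incidence rates by INR level, TTR category and "other covariates during the first 90 days after initiation of warfarin treatment", and hazard ratios by INR level and TTR category.
- Secondary objective 3 (section 4.1.2) estimates incidence rates after warfarin has stopped.
- Exploratory objective 2 (section 4.1.3) estimates incidence rates from two weeks before to two weeks after a procedure. It continues: "Also, an indicator variable of the discontinuity period will be added to the Cox's proportional hazards model".

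**The concern.** The variable is meant to show whether a patient is on another anticoagulant. A code list narrower than its label misclassifies in one direction: a patient who buys a heparin outside the two listed codes is recorded as having none.

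Starting, interrupting or stopping warfarin is where knowledge of other anticoagulant cover matters most for reading event rates. If some of these patients are covered by heparin and the data cannot show it, rates described as off warfarin or early in treatment mix covered and uncovered time, and the two cannot be separated.

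Timing adds to this. How a covariate enters a model can be settled in the statistical analysis plan. Which purchases are extracted is settled by the data request, which is based on the protocol. Section 4.1 promises the analysis plan only before any analysis is performed, which may be after the data have arrived.

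**Working it through.** The plan states no figure on this point, so the check is a comparison of its code lists.

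1. **Which codes are listed.** Section 3.4.2 gives B01AB01 and B01AB51 for heparins. It has no group-level entry B01AB and no other code in that group.

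2. **What a 01/51 pair means in this protocol.** In Appendix 3, Table 1, C01BA01 is quinidine and C01BA51 is "quinidine, combinations excl. psycholeptics". In Table 3, ibuprofen is M01AE01 and M01AE51, and cimetidine is A02BA01 and A02BA51. In each case the pair is one substance, alone and in combination. Read the same way, B01AB01 and B01AB51 are one heparin and its combinations.

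3. **Whether the rest of the group appears elsewhere.** Section 3.4.3 names no heparin. Appendix 3, which is titled as the list of ATC codes in the study, contains no B01AB code at all. No low-molecular-weight heparin appears by name or code anywhere. That these agents sit under other codes in B01AB follows from the ATC classification the protocol uses, not from a sentence in the protocol.

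4. **What the study can observe.** Drug data are register purchases, and in-hospital drugs are unavailable. Outpatient purchases are therefore the only heparin exposure the study can see. Under the current list it would see those of one substance and its combinations.

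5. **Where it bears on the analyses.**
   - Secondary objective 1 plans both rates and hazard ratios by INR category in the first 90 days.
   - Secondary objective 3 plans rates only, within strata of other covariates. A patient who moved to another heparin counts simply as having stopped warfarin.
   - Exploratory objective 2 plans rates by other covariates and a discontinuity indicator. No heparin term is named.

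6. **Size.** The protocol gives no number of heparin purchasers, no number of procedures and no share of time under heparin cover. No effect size follows. The power table in section 4.2 does not use this variable and is unchanged.

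**The case against.** The strongest reply is that this is one component of a secondary variable and that little hangs on it. Several parts of that reply stand.

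- **No model names the term.** Sections 4.1.1 to 4.1.3 adjust for other covariates, which is the heading of section 3.4.3, and heparin is not listed there. Widening the codes alone might change no hazard ratio.
- **Usual-care rates may be the target.** Section 1.1 describes the study as real-world evidence on current practice. A rate after stopping warfarin is not wrong because some patients had other cover. It is only less informative when that cover cannot be seen.
- **Appendix 3 is incomplete in general.** It also lacks clopidogrel, dipyridamole and prasugrel, so its silence says nothing specific about low-molecular-weight heparins.
- **The in-hospital gap is already declared**, in general terms, in section 5.

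A reader might infer more: that the listed codes are drugs given mainly in hospital, that the variable will be almost empty, or that most patients with interrupted warfarin receive heparin as a bridge. The protocol says none of this and never mentions bridging.

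A reader might also infer that the INR below 2.0 versus 2.0-3.0 hazard ratios are distorted enough to hide or create the 10-20% differences of section 4.2. That would need assumptions with no anchor in the protocol. Suppose that heparin covers 10-30% of early low-INR time and halves stroke risk. The stroke rate in that window then falls by 0.10 × 0.5 = 5% to 0.30 × 0.5 = 15%. But section 4.2 is powered on whole-cohort time. Suppose further that all 32,000 patients were new users, with half their first 90 days below 2.0:
- 32,000 × 90/365.25 ≈ 7,900 person-years, of which half is about 3,940.
- 3,940 / 21,000 ≈ 19% of all time below 2.0.
- The stroke rate of the whole category then moves by 0.19 × 5% ≈ 1% to 0.19 × 15% ≈ 3%.

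This is an illustration, not an estimate or a bound. It shows that a figure for a sub-window cannot be set against the whole-cohort power.

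What the reply does not answer is the mismatch itself. The protocol gives no reason for restricting heparins to one substance, and a code that is not requested cannot be restored by the analysis plan.

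**Conclusion.** The point holds as a defect in a code list. The heparins component covers one substance and its combinations, so other heparins bought by outpatients would be missed and the buyers coded as unexposed on it. It is relevant to secondary objectives 1 and 3 and exploratory objective 2. It does not touch the INR exposure, the endpoints or the power calculation, and no bias in the primary hazard ratios is shown. Its size cannot be derived from the protocol.

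The conclusion rests on three assumptions: the two codes have the meaning that the protocol's other 01/51 pairs have; the register request follows the lists in the protocol; and other heparins are bought in a way that the Prescription Register records. Section 5 puts the register's coverage at about 97%, with relatively inexpensive, non-reimbursed packages missing.

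**What to change.** - In section 3.4.2, replace the two heparin codes by the whole group B01AB, or state why only one substance is wanted.
- Add all the codes of this variable to Appendix 3, so that the two lists agree and the data request covers them.
- Report the secondary objective 3 rates and the discontinuity-period analysis of exploratory objective 2 with and without time covered by heparin purchases.

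The cost is a slightly wider code range in the same request to the register holder and a small amount of extra analysis. No primary definition changes. Control remains partial: heparin given in hospital stays unobserved, as the general limitation in section 5 already implies.

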3.4.3 Other Covariates/Control Variables

- Reimbursement code 207
 - Yes/no
- Information about hospitalizations and institutionalization (other than hospitalization)

- dates
- will be taken into account when defining the discontinuation of warfarin treatment
- Laboratory parameters for anemia characterizations
 - Blood picture
 - ◆ Haemoglobin
 - decrement of 20 g/L
 - being under the reference value
 - See [Appendix 2](#) for details.
- Concomitant use of class D interactive drugs according to SFINX (Swedish, Finnish, INteraction X-referencing, see [Appendix 3, Table 3](#) for complete ATC listing)
 - Concomitant use during the warfarin treatment period assumed by the purchases and exposure (see definition for exposure in Section 4.1).
- Age*
- Gender*
- Hospital district
 - Helsinki, Turku, Tampere, Kuopio, Oulu, Jyväskylä
 - other possible central hospitals
- CHADS₂^{11 12}
- CHA₂DS₂-VASc^{11,12}
- Comorbidities (more in detail in [Appendix 4](#))
 - Hypertension*
 - Thyrotoxicosis
 - Cardiomyopathy
 - Congestive heart failure*
 - Diabetes*
 - Stroke*
 - Transient ischemic attack*
 - Vascular disease**
 - Cancer
 - Venous thromboembolism
 - *included in CHADS₂ score and in CHA₂DS₂-VASc score
 - **included in CHA₂DS₂-VASc score.

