4 STATISTICAL ANALYSIS

4.1 Statistical Analysis Methods

Data management, tabulations, graphics, and statistical modeling in carried out with R language (<http://www.r-project.org>). R language is described more detailed in report "R: Regulatory

Compliance and Validation Issues: A Guidance Document for the Use of R in Regulated Clinical Trial Environments" (<http://www.r-project.org/doc/R-FDA.pdf>)

A separate statistical analysis plan (SAP) including detailed statistical analysis and outputs will be produced by EPID research prior to performing any analysis.

Study population: The study population will be described at baseline (start of follow-up) using by previous drug exposure and other covariates.

Study outcomes: All study outcomes will be summarized by drug exposure and other covariates.

Drug exposure: Drug exposure starts at date of purchase. The length of the exposure period is calculated as $DDD/dose \times 1.5$, where DDD (daily defined dose) is the total amount purchased and “dose” is the amount used daily (one for an average person). For the first purchase “dose=1” and for other purchases the “dose” is calculated from previous use by dividing the previous DDD with the time between the present and the previous purchase.

The impact of the multiplier 1.5 in the construction of drug exposure will be evaluated for the primary objectives in sensitivity analyses by using multiplier values 1.25, 1.5 and 2. We will also perform a sensitivity analysis for the primary objectives by including only those patients with at least two purchases of prescriptions within a clinically meaningful timeframe of 3 months after the index date.

INR levels: Daily INR levels are calculated:

- 1) As the previous recorded INR measurement
- 2) By linear interpolation between two consecutive INR measurements. If the gap between the measurements is more than 60 days the previous measurement is applied.

Daily INR estimates are categorized into levels: under 2.0, 2.0-3.0, over 3.0. In addition when appropriate a finer categorization is used: under 1.5, 1.5-2.0, 2.0-3.0, 3.0-4.0, 4.0-5.0, 5.0-9.0, and over 9.0. This finer categorization will be used only in the analysis of the primary objectives.

Time in therapeutic range (TTR): The INR target value for AF patients is 2.0-3.0. In addition for stroke, systemic thromboembolic events, and myocardial infarction INR target above 2.0 is considered and for bleeding events INR target under 3.0 is considered.

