dexibuprofen	M01AE14		
dexketoprofen	M01AE17		
diclofenac	M01AB05	M01AB55	
etodolac	M01AB08		
flurbiprofen	M01AE09		
ibuprofen	M01AE01	M01AE51	C01EB16
indometacin	M01AB01	M01AB51	C01EB03
ketoprofen	M01AE03	M01AE53	
ketorolac	M01AB15		
lornoxicam	M01AC05		
meclofenamic acid	M01AG04		
mefenamic acid	M01AG01		
meloxicam	M01AC06	M01AC56	
nabumetone	M01AX01		
naprokseeni	M01AE02	M01AE52	M01AE56
niflumic acid	M01AX02		
niesulide	M01AX17		
phenylbutazone	M01AA01	M01BA01	
piroxicam	M01AC01		
sulindac	M01AB02		
tenoxicam	M01AC02		
tiaprofenic acid	M01AE11		
tolfenamic acid	M01AG02		
Coxibs:			
celecoxib	M01AH01	L01XX33	
etoricoxib	M01AH05		
lumiracoxib	M01AH06		
rofecoxib	M01AH02		
parecoxib	M01AH04		
valdecoxib	M01AH03		

Other analgetics:

Table 3: Class D interactive drugs according to SFINX

acetylsalicylic acid	B01AC06	M01BA03	N02BA01	N02BA51	N02BA71
diflunisal	N02BA11				

Drugs raising bleeding risk by increasing warfarin exposure (and INR):

Antifungals:

ekonatsoli	D01AC03	G01AF05				
fluconazole	J02AC01					
metronidazole	A02BD01	A02BD02	A02BD03	A02BD08	J01XD01	P01AB01
miconazole	A07AC01	J02AB01				
sulfamethoxazole	J01EC01	J01EE01				

Miscellaneous:

cimetidine	A02BA01	A02BA51			
clofibrate	C10AB01	C10AB03			
fluvoxamine	N06AB08				
noscapine	R05DA07				
silymarin	A05BA03				
tramadol	N02AX02	N02AX52			

Drugs increasing the risk of embolism by decreasing warfarin exposure (and INR):

colestyramine	C10AC01
mitotane	L01XX23

ATC=Anatomical Therapeutic Chemical; INR=international normalized ratio; NSAIDs=non-steroidal anti-inflammatory drugs.

Source: 1.) SFINX Drug database. Class D interactive drugs. Accessed February 18, 2013. Available at: http://www.medbase.fi/sfinx/whatis_finx.htm. and 2.) WHO Collaborating Centre for Drug Statistics Methodology. ATC/DDD Index. December 2012. Available at: http://www.whocc.no/atc_ddd_index.

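### Section 3.4.3 times interacting drugs with a refill rule that assumes continuous use, so a repeated short course is given 1.5 times the preceding interval as exposure

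*Protocol*

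**What the plan says.** Section 3.4.3 lists concomitant use of SFINX class D drugs among the covariates and times it as follows: "Concomitant use during the warfarin treatment period assumed by the purchases and exposure (see definition for exposure in Section 4.1").

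Section 4.1 holds one exposure definition, under the general heading Drug exposure. "Drug exposure starts at date of purchase", and the length of the period is DDD/dose × 1.5. The numerator counts everything bought at that purchase; the divisor, dose, "is the amount used daily (one for an average person"). The first purchase has dose = 1. For every later purchase the dose "is calculated from previous use by dividing the previous DDD with the time between the present and the previous purchase". The section gives no longest allowable interval, no return to dose = 1 after a gap, and no separate rule for drugs taken in short courses.

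The drugs concerned are in Appendix 3, Table 3. They include a long list of NSAIDs, tramadol, and, under the heading "Drugs raising bleeding risk by increasing warfarin exposure (and INR"), fluconazole, metronidazole and sulfamethoxazole.

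On robustness, Section 4.1 says: "The impact of the multiplier 1.5 in the construction of drug exposure will be evaluated for the primary objectives in sensitivity analyses". The alternatives to 1.5 that it names are 1.25 and 2.

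**The concern.** The refill rule suits a drug taken every day. If the previous pack lasted until the next purchase, pack divided by interval is a fair estimate of daily use. For an anti-infective course or an as-needed analgesic, most of the interval is time off the drug. The rule reads that drug-free time as very slow daily dosing and carries it forward to the next pack.

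The variable is used in three places. The covariates of Section 3.4.3 stratify the incidence rates and enter the Cox models (Sections 4.1.1 to 4.1.3). Exploratory Objective 6 tabulates interacting-drug use at the start of and during follow-up, the latter also by INR and TTR level. If finished courses count as current use, on-drug rates are pulled towards off-drug rates, adjustment for these drugs is weakened, and baseline use is overstated.

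**Working it through.** The protocol gives no figure for the duration of interacting-drug use, so there is none to reproduce. The check applies the Section 4.1 rule as written and then asks how far it could dilute a rate comparison.

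**1. Length given to a repeat purchase**

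Inputs from Section 4.1: length = DDD/dose × m, with m = 1.5; dose = 1 at the first purchase, and previous DDD/interval afterwards. Assumed: a one-week course of 7 DDD, repeated after 365 days.

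- First purchase: 7/1 × 1.5 = 10.5 days.
- Second purchase: dose = 7/365 = 0.0192 DDD a day; length = 7/(7/365) × 1.5 = 547.5 days (18.0 months).
- Both together: 10.5 + 547.5 = 558 days, for about 14 days of drug at 1 DDD a day.

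For two equal packs of size D bought G days apart, D/(D/G) × 1.5 = 1.5 × G. Pack size cancels, so packs of 3.5, 7, 10 and 14 DDD all give 547.5 days.

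| Change from the base case | Length of second purchase |
|---|---|
| Interval 90 days | 135 days |
| Interval 180 days | 270 days |
| Interval 730 days | 1,095 days |
| Second pack half the first | 9.0 months |
| Second pack double the first | 36.0 months |
| Multiplier 1.25 | 456 days |
| Multiplier 2 | 730 days |

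The planned multiplier analysis only rescales the result, because the source of the error is the interval. It is also confined to the primary objectives.

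**2. Dilution among occasional purchasers**

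Assumptions, none from the protocol: purchases at random times, drug taken at 1 DDD a day, two years of purchase history, four years of follow-up, true rate ratio 2.0 while on drug.

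If a fraction p of labelled time is real and almost all true exposure lies inside labelled time, the apparent rate ratio is close to p × 2 + (1 − p) × 1 = 1 + p.

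- One 10-DDD pack a year: true exposure = 10/365 = 2.7% of time. By simulation, about 67% of time is labelled exposed. Then p = 2.7/67 = 4%, and the apparent ratio is about 1.04.
- Over 0.5 to 2 purchases a year and packs of 7 to 30 DDD: 40-82% of time is labelled, 2-18% of it real, and the apparent ratio is 1.02-1.18.

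**3. Dilution with regular users in the mix**

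Further assumption: some users buy 100 DDD about every 100 days, and the rest are occasional purchasers as above.

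| Regular users | Occasional purchases per year | Labelled time that is real | Apparent ratio |
|---|---|---|---|
| 20% | 1 | 29% | 1.29 |
| 20% | 0.3 | 49% | 1.49 |
| 30% | 0.3 | 62% | 1.62 |

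**4. Alternatives, one 10-DDD pack a year**

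- A 150-day cap on every exposure period: 31% of time labelled, 9% of it real, apparent ratio 1.09.
- Each purchase timed on its own (dose = 1, multiplier 1.5): 4.0% labelled, 67% of it real, apparent ratio 1.67. The shortfall from 2.0 comes from the multiplier, since 10 of every 15 labelled days are real.

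**5. Possible effect on an INR hazard ratio**

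Take true exposure of 2.7% and a rate ratio of 2.0, and leave the drug wholly unadjusted. If use is twice as common in one INR category, the hazard ratio shifts by (1 + 0.054)/(1 + 0.027) = 1.026. If it is three times as common, the shift is (1 + 0.081)/(1 + 0.027) = 1.053.

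**The case against.** **The cross-reference may mean only the warfarin period.** The sentence in Section 3.4.3 can be read so that Section 4.1 defines the warfarin treatment period, with interacting use taken from purchases alone. Parts of Section 4.1 are plainly built for warfarin, such as the two-purchase check tied to the index date. This reading is possible. But the sentence is about class D drugs, the rule is headed Drug exposure without restriction, and the narrower reading leaves these drugs with no timing rule at all. The sentence needs correcting either way.

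**The year-apart example is a chosen case.** It needs equal packs and enough remaining warfarin treatment and follow-up for the 548 days to run. This is right as far as it goes, but the factor of 1.5 times the interval holds for equal packs at any spacing.

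**Table 3 also holds drugs that can be bought regularly**, such as acetylsalicylic acid, coxibs and colestyramine. For regular refills the rule behaves acceptably. A reader might infer from the occasional-purchaser figures that most labelled person-time in the whole cohort is unexposed, or that adjustment achieves almost nothing. The protocol gives no purchase patterns to support that, and step 3 shows smaller dilution once regular users are included.

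**The primary results may hardly move.** A reader might also infer that the INR hazard ratios are compromised. That is not shown: step 5 gives shifts of 1.026 to 1.053 even with no adjustment. For the drugs that Table 3 says act through INR, closer adjustment is not clearly an improvement either.

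**Objective 6 is exploratory and yes/no.** A patient-level tabulation of any use during follow-up would change little. Use at the start of follow-up, and any tabulation by person-time within INR or TTR level, would be affected.

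**Detail is deferred to a separate SAP.** That plan might add a cap, but the protocol already fixes a rule, and followed as written it mislabels intermittent use.

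**Conclusion.** The point holds for intermittently bought drugs. The rule that Section 3.4.3 invokes gives a repeat purchase of equal size 1.5 times the preceding interval, 548 days after a one-year gap, subject to truncation at the end of warfarin treatment or follow-up. That arithmetic rests only on Section 4.1 and the chosen interval.

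The size of the dilution rests on assumed purchasing. For a true rate ratio of 2.0, the apparent ratio is about 1.04 for one 10-DDD pack a year among occasional purchasers only, and about 1.3-1.6 when 20-30% of users refill regularly. The consequence is biased rates by interacting-drug use, weaker adjustment for it, and distorted baseline and person-time tabulations for Exploratory Objective 6. It should be corrected before analysis, but no material error in the primary INR comparisons has been demonstrated.

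**What to change.** In Sections 3.4.3 and 4.1, limit the refill-derived dose to warfarin. For Table 3 drugs, time each purchase separately: exposure starts on the purchase date and lasts the purchased DDDs at dose = 1, times 1.5. This is what the rule already does for a first purchase; two 7-DDD courses would then count 2 × 10.5 = 21 days instead of 558. A cap chosen to suit warfarin refills is not a substitute, as the 150-day example shows. A fixed exposure window could be added as an optional sensitivity analysis.

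The cost is a sentence in the protocol and a change in the exposure code, with no new data. The downside is that exposure will be somewhat short for patients who take a Table 3 drug continuously at less than 1 DDD a day.
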